3.9.3 Procedures for discontinuation of a patient from investigational product

Patients permanently discontinuing study medication should be given conventional therapy, if applicable, and should always be asked to continue the regular study visits as described below.

A patient who decides to discontinue study medication will always be asked about the reason(s) to discontinue study medication and the presence of AEs (if any). These data will be ascertained and documented by the investigator and recorded in the eCRF as appropriate. AEs will be followed up (see Sections 4 and 6.4); and the patient should return all study medications.

Discontinuation from study medication is not the same as complete withdrawal from the study (withdrawal of consent), which has a direct impact on the potential validity of all study data, and should be avoided wherever possible. It is essential to collect as much data as possible for all patients throughout the study and especially all potential endpoint events.

All discontinued patients unless consent withdrawal will be followed up for vital status and hospitalizations until study closure (see Section 3.9.3.2).

If the patient permanently discontinues study medication prior to closure of the study, there should be several different options for their continuation in the study as described below:

3.9.3.1 Patient agrees to undergo the Premature Treatment Discontinuation Visit and then continue in-person study visits

The patient agrees to undergo the Premature Treatment Discontinuation Visit (PTDV) and then continue in-person study visits according to plan. This is the **preferred** option and patients who discontinue study medication will always be asked if they agree to this approach. If agreed, as above, the patient will undergo their PTDV within 15 days after the study medication is stopped. The PTDV includes the same assessments as the EOT visit. The patient will continue attending subsequent study visits according to schedule (Table 1), or if needed with reduced frequency until end of study is declared (i.e., when the prespecified number of primary events has been reached). The patient will then return for their EOS visit **as soon as feasible**, but no later than 60 days after the study closure has been declared. It is essential that the patients attend the EOS visit in person whenever possible.

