3.9.3.4 Restart of study medication

Whenever possible, restart of randomized study medication should be encouraged. However, if a patient has permanently discontinued study drug and a PTDV has been performed, study drug should not be restarted.

If patient has been treated with erythropoietin analogue as rescue, see [Section 7.7.4](#) for guidance on when study drug treatment can be restarted.

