4. STUDY PLAN AND TIMING OF PROCEDURES

During study visits, all assessments including laboratory tests and physical examinations should be completed prior to initiation of the hemodialysis (HD) procedure in patients receiving HD. The EQ-5D-5L quality of life assessments should be completed prior to any intervention (e.g., start of dialysis in HD patients) and at approximately the same time of the day. Blood samples for Hb measurement and safety laboratory tests will be obtained according to Study Plan, [Table 1](#).

Table 1 Study Plan

	Screening ^a		Treatment (-4d to +2d)																								EOT (-4d to +2d)	EOS (4wks after EOT+4d)	
	Up to 6 wks		Rand (wk 0)	wk 1 	Wk 2	4	6	8	10	12	14	16	18	20	24	28	32	36	40	44	48	52	56	60	every 4 wks				
Visit^o	1	2	3	4	5	7	9	11	12	13	14	15	16	17	18	19	20	21	22	23	24	25	26	27	etc				
Written informed consent	X																												
Eligibility criteria	X	X	X																										
Demographics and medical history	X																												
Physical examination	X ^b		X							X ^b					X ^b													X	
Height ^c , weight ^d	X		X							X					X			X					X				every 24 wks ^t	X	
12-lead ECG			X							X					X													X	
Blood pressure, Heart rate	X ^e	X	X ^{e,q}			X		X		X ^e		X		X	X ^e	X	X	X	X	X	X	X	X ^e	X	X		X, every 24 wks X ^{e,t}	X ^e	
Renal ultrasound if none performed within 12 weeks prior to randomization		X																											
Serum hCG pregnancy test ^f	X		X							X				X		X		X		X		X		X			every 8 wks	X	

Table 1 Study Plan

	Screening ^a		Treatment (-4d to +2d)																								EOT (-4d to +2d)	EOS (4wks after EOT+4d)
	Up to 6 wks		Rand (wk 0)	wk 1 	Wk 2	4	6	8	10	12	14	16	18	20	24	28	32	36	40	44	48	52	56	60	every 4 wks			
Visit^o	1	2	3	4	5	7	9	11	12	13	14	15	16	17	18	19	20	21	22	23	24	25	26	27	etc			
Serology (HIV, Hepatitis B and C), Vitamin B12, folate	X																											
Hemocue assessment ^g	X	X	X		X	X	X	X	X	X	X	X	X	X	X	X	X	X	X	X	X	X	X	X	X	X	X	
Hemoglobin (Central lab)		X			X		X	X	X		X	X	X	X		X	X	X	X	X	X		X	X	X	X	X	
Complete blood count (CBC) ^h	X		X			X				X					X								X				X	

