- k After suspected CSE event (MI, stroke, unstable angina, heart failure, DVT, PE, hypertensive emergency or vascular access thrombosis), collect EQ-5D-5L at next regularly scheduled visit.
- l Baseline dialysis related signs and symptoms will be recorded at randomization and AEs will be recorded starting from the first dose administration
- m Dose adjustment review every 4 weeks. Hemocue values measured from venous blood samples, collected in lavender tube, will be used for all dose adjustments with baseline value from Hemocue values at randomization. In the event of excessive erythropoiesis dose can be adjusted at any time see Section [7.2.3.4](#).
- n Dispensation every second week from Day 1 to week 20, every 4 weeks thereafter. In the event of excessive erythropoiesis dose can be adjusted at any time see Section [7.2.3.4](#).
- o Please be attentive to visit # which are not consecutive due to removal of some visits from Study plan
- p PK sampling is done only for patients assigned to the roxadustat treatment arm.
- q Refer to exclusion criterion 1: if ANY of the 3 measurements is exclusionary before dialysis on the day of randomization, then a BP measurement should be done after dialysis to confirm eligibility.
- r Receipt of the first dose of study drug defines Study Day 1.
- s Randomization may occur up to 2 weeks after the screening period ends, in order to allow for synchronization with the patient`s existing dosing schedule
- t Every 24 weeks should be calculated from week 48 for Intact parathyroid hormone (PTH) and from week 52 for Weight, Blood pressure/Heart rate and EQ-5D-5L.

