4.2 Treatment period

Procedures will be performed according to the Study Plan in [Table 1](#).

The treatment period begins on the first day of dosing with study treatment (Day 1, week 0). Day 1 is preferably a scheduled treatment date according to the existing erythropoietin analogue treatment regimen.

The first day of dosing should not occur less than 2 days from the last dose of epoetin alfa or epoetin beta, less than 7 days since the last dose of darbepoetin alfa or less than 14 days since the last dose of Mircera[®]. All Day 1 study assessments are to be performed prior to first study drug administration; in hemodialysis patients, study assessments should also be performed prior to or at initiation of the dialysis procedure for patients treated with epoetin alfa prior to randomization.

During the treatment period, the patient will be contacted by telephone at week 1. Patient will attend study visits every 2 weeks from randomization to week 20 and every 4 weeks thereafter until study closure is declared. The patient's next scheduled visit will then be the EOT visit, marking the end of the treatment period. At the EOT visit, the physicians caring for the patient will decide upon treatment the patient should receive as part of his/her ongoing clinical care.

The study is event-driven and will be closed when the target number of CV events has been accrued. Treatment duration is estimated to be up to 4 years.

In case of premature discontinuation of study medication, see Section [3.9](#).

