7. INVESTIGATIONAL PRODUCT AND OTHER TREATMENTS

7.1 Identity of investigational product(s)

Table 3 Identity of investigational product

Investigational product	Dosage form and strength	Manufacturer
Roxadustat	Oral tablets 20mg, 50mg and 100mg	FibroGen

The formulation number and batch number will be recorded in the study master file and identified in the clinical study report (CSR).

The only epoetin alfa to be used in the study is Procrit[®], Eprex[®] and Epogen[®], will be reimbursed in countries where this is possible, or otherwise centrally supplied by AstraZeneca.

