4.1 General principles

All study data will be listed by treatment group, centre, and subject number. Throughout subject data listings, figures and tables, treatment groups will be labelled as “Roxadustat” and “Epoetin alfa”.

Study Day will be listed in all data listings whenever an assessment date is presented. Study Day is a relative number, relative to the date of first dose of study drug. Week is also a relative number, relative to the number of weeks from the first dose of study drug. Study Days 1-7 is defined as Week 0, Days 8-14 as Week 1, etc. Clinical events and other variables reported after the EOT visit for a subject will not be included in the primary efficacy and safety

analysis. If collected, these events will be included in tables. Events that are recorded as beginning prior to the date and time of randomization will not be included in a listing.

In addition to specific analyses and presentations that are detailed in the following sections, results will be summarised using descriptive statistics, including the number of subjects (n), mean, standard deviation (SD), median and range (i.e. minimum and maximum) as appropriate. For categorical variables counts and percentage n (%) per treatment group will be presented. Summaries of continuous variables will be based on non-missing observations. For time to event data, the number and percentage of subjects recording the event will be summarised. Ninety-five percent confidence intervals will also be included where appropriate, as a measure of precision. Demographic characteristics, qualifying risk factors and other specific medical and surgical history will be summarised for the ITT analysis set using descriptive statistics. Mean Hb values over time will be graphically displayed and grouped by treatment.

Dates will be presented in the format YYYY-MM-DD.

When the last dose date is missing, it will be imputed as the earliest date of last drug dispense date + number of days of drug dispensed, date of death, date of EOT visit or date of EOS visit.

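### The rule for a missing last-dose date omits the premature discontinuation visit, so a subject can be imputed as on drug after a visit showing the drug was stopped

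*SAP*

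**What the plan says.** SAP 4.1 has a fallback for subjects with no recorded last dose: "it will be imputed as the earliest date of last drug dispense date + number of days of drug dispensed, date of death". Two further candidates close the list, namely the EOT and EOS visits. SAP 6.1 lists the rule as new in this edition, added to deal with missing last dose dates.

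The protocol has a further visit for subjects who stop early. Under 3.9.3.1, "the patient will undergo their PTDV within 15 days after the study medication is stopped". Under 3.9.3.4, "if a patient has permanently discontinued study drug and a PTDV has been performed, study drug should not be restarted". The PTDV and the EOT visit are described separately. On content, "The PTDV includes the same assessments as the EOT visit". On timing, Protocol 4.2 says that once study closure is declared the next scheduled visit "will then be the EOT visit, marking the end of the treatment period".

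On supply, footnote n of the protocol's Table 1 gives the schedule: "Dispensation every second week from Day 1 to week 20, every 4 weeks thereafter".

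**The concern.** A PTDV held as the protocol describes is an upper bound on the last dose: drug has already stopped and may not be resumed. The rule does not use that bound. For a surviving early discontinuer, EOT and EOS come at study closure, possibly years later, so the end of the dispensed supply is the only early limit. The imputed last dose can then fall on a date that the protocol rules out.

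The last-intake date matters in several places:
- censoring for OT+0, OT+3 and OT+7 (SAP 2.1.3, 4.1.1);
- the 7-day cut-off for treatment-emergent events (SAP 4.3.8.1);
- PPS censoring, and the requirement that a valid Hb be taken no more than three days after last intake (SAP 2.1.2). The PPS carries the EU primary endpoint, which is the first FDA secondary;
- the last confirmatory step, time to first RBC transfusion on OT+3 with a hazard-ratio margin of 1.8 (SAP 4.3.4).

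Protocol 3.9.3 has discontinued subjects receive conventional therapy where applicable and asks them to keep attending visits. A late imputed date could therefore admit off-drug Hb values and events as on-drug data, unless another deviation rule removes them.

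**Working it through.** The plan gives no count of missing last-dose dates and no expected error, so it has no figure of its own to reproduce. The check is a day count under the rule as written.

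**Inputs.** Supply interval D: 14 days to week 20, 28 days afterwards (Protocol Table 1, footnote n). Visit window: -4 to +2 days (Table 1), so two 4-weekly visits can be 28 + 4 + 2 = 34 days apart. Delay v from stop to PTDV: 0 to 15 days (Protocol 3.9.3.1).

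**Formulas.** Let s be the days from last dispensing to stop.
- Overrun past the true last dose = D - s.
- Part falling after the PTDV = max(0, D - s - v).
- Overrun with the PTDV in the list = min(D - s, v), so at most 15 days.

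**One record.** A 28-day supply is dispensed on day 197, drug is stopped on day 201 and the PTDV is on day 205. The rule gives 197 + 28 = day 225, which is 24 days after the last dose and 20 days after the PTDV. OT+3 then ends on day 228 instead of day 204. With the PTDV listed, the imputed date is day 205, an error of 4 days.

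**Largest overrun beyond the PTDV (s = 0).**

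| Supply interval | PTDV same day | PTDV 7 days later | PTDV 15 days later |
|---|---|---|---|
| 14 days | 14 | 7 | 0 |
| 28 days | 28 | 21 | 13 |
| 34 days (supply covers the window) | 34 | 27 | 19 |

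**Average size, on assumptions not in the documents.** Take D = 28, s uniform on 0-28, v uniform on 0-15, and a PTDV for everyone.
- Probability that the imputed date is after the PTDV: 1 - 7.5/28 = 73%.
- Mean days after the PTDV over all such records: (28³ - 13³)/(3 × 15 × 2 × 28) = 19,755/2,520 = 7.84. Among overrunning records: 7.84/0.732 = 10.7 days.
- Mean error: 14.0 days as written, and 14.0 - 7.84 = 6.2 days with the PTDV listed.

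**Total exposure.** If 1-3% of 2000 subjects (20-60) had such a record, the time wrongly counted after the PTDV would be 20 × 7.84 = 157 days to 60 × 7.84 = 470 days, or about 0.4 to 1.3 patient-years.

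**Conditional case: epoetin with no dispense record.** The rule then falls to EOT or EOS. With EOT at 4 years (4 × 365.25/7 = 208.7 weeks), a stop at week 28 is carried 180.7 weeks to EOT, or 184.7 weeks to EOS.

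To see what this could do to the transfusion hazard ratio, suppose a mean of 1.5 years on treatment, 3 extra years per affected epoetin subject, and an off-drug transfusion rate k = 1 to 2 times the on-drug rate. With a fraction m of epoetin subjects affected, the epoetin rate is multiplied by r = (1.5 + 3km)/(1.5 + 3m), and a true ratio of 1.80 appears as 1.80/r:
- m = 0.5%: 1.78 to 1.80
- m = 1%: 1.765 to 1.80
- m = 5%: 1.65 to 1.80

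**The case against.** The strongest reply is that the rule will seldom be needed. Protocol 3.10 requires the date of last intake to be documented, and 7.2.1 and 7.5 require doses given to be recorded in the eCRF. A subject who attends a PTDV is also the one whose stop date a site can most easily record; dates are more likely to be missing in subjects who refuse visits or are lost, and for them a PTDV cap does nothing. This stands, and it limits the number affected. It does not make the rule right for those it reaches.

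A second reply is that EOT may already mean the PTDV. The contents are the same, the protocol's Table 1 has no PTDV column, 3.9.3.1 takes the subject from the PTDV through scheduled visits to EOS without a separate EOT, and the SAP never uses the term. If the data are stored that way, the bound already exists. But Protocol 4.2 ties EOT to study closure and nothing equates the two visits, so the SAP has to say which is meant.

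Third, the reach is limited. The US primary analysis uses the ITT set and does not depend on last dose, and the transfusion endpoint is repeated on ITT (SAP 4.3.6). Both points are correct.

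A reader might go further and infer that epoetin subjects are carried to study end, giving an error that differs by arm. Protocol 7.1 says epoetin "will be reimbursed in countries where this is possible, or otherwise centrally supplied by AstraZeneca", and the dispensation text in 7.2.1 names only tablets and sponsor-supplied epoetin. The documents do not support that step. SAP 3.4 records dispensed and returned study medication without limiting arm or supply route, important deviation 1 in SAP 2.2 relies on the same comparison, and the study-plan row for dispensing has no arm restriction. Nowhere is reimbursed epoetin said to lack a dispense record.

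**Conclusion.** The concern holds as a gap in the stated rule. As written, SAP 4.1 can place the last dose after a visit that shows the drug was stopped, unless the PTDV is stored as EOT.

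The 14-, 28- and 34-day figures are upper limits; the overrun past the PTDV can be zero. The averages rest on assumed uniform timings, a 28-day supply and a PTDV for everyone. The count of affected subjects is unknown, and the 1-3% is an assumption.

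An overrun of years, and a difference between arms, remain possible only if an epoetin subject lacks both the last-dose date and a dispense record. Even then, with 1% of epoetin subjects affected, the illustrated shift from a true hazard ratio of 1.80 is at most to about 1.765. The case for amending is that the windows become more accurate at almost no cost, not that a confirmatory result is likely to change.

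**What to change.** Amend the rule in SAP 4.1 before database lock:
- Add the PTDV date to the earliest-of list, or state that the PTDV counts as the EOT visit for this rule. If the second route is taken, confine it to this rule: SAP 4.1 also leaves variables reported after a subject's EOT visit out of the primary efficacy and safety analysis, whereas SAP 4.1.1 follows ITT subjects to EOS whether or not they have stopped drug.
- Where the eCRF holds a last recorded administration date, use that date itself as the last dose. Adding a dosing interval would put the last dose later than the recorded one.
- Report the number of imputed last-dose dates by arm, so that readers can judge how far the on-treatment and per-protocol results rest on them.

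The cost is a few SAP sentences, one extra term in the date derivation and one summary table. No new data collection should be needed, since the PTDV is a protocol visit and administration is already to be recorded.

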4.1.1 Censoring

For analyses based on OT+7, subjects will be censored at 7 days after last intake of study drug, or the EOS visit, whichever is earliest.

For analyses based on OT+3, subjects will be censored at 3 days after last intake of study drug, or the EOS visit, whichever is earliest.

For analyses based on OT+0, subjects will be censored at last intake of study drug, or the EOS visit, whichever is earliest.

For analyses based on the ITT analysis set and FAS, subjects will be censored at their individual EOS visit, regardless of if they have discontinued study drug or not. Complete endpoint information will be pursued with every effort for all subjects, unless they exercise their right to withdraw consent. Subjects who withdraw consent will be censored at date of withdrawal of consent, and subjects who are lost to follow up (LTFU) will be censored at last available contact.

Subjects who withdraw consent and for whom only vital status (known to be alive at study closure, or date of death) may be obtained from public records, the occurrence of all components of the primary endpoint cannot be assessed, and will thus be censored at date of consent withdrawn for all analyses. However, the determination of all-cause death will utilize all publicly known mortality data, even that extending beyond date of consent withdrawal. The vital status information will be included in the analysis of all-cause death as a single endpoint, and in sensitivity analysis and tabulations. Similarly, complete information on the endpoint may not be obtained for subjects who are LTFU. Any such subject will be censored in the analysis at the last contact where all elements of the endpoint were assessed. A subject

will not be recorded as LTFU until the end of the study, after every allowable effort to get in contact has been made. Hence, it is anticipated that the number of subjects LTFU will be limited.

4.1.2 Premature permanent discontinuation of study medication

Premature discontinuation from study medication is not the same as withdrawal from the study. As described in Section 3.9 in the CSP there are several options for continuing the study.

It is expected that complete information on the safety composite endpoint events, and as much as possible of the remaining eCRF data, will be obtained for all subjects who prematurely discontinue study medication, unless they refuse any form of follow-up and withdraw consent or are LTFU.

4.1.3 Choice of the non-inferiority margins

Non-inferiority for the Hb efficacy endpoint will be established if the lower limit of the two-sided 95% CI for the difference between the means of the primary endpoint (roxadustat minus control epoetin alfa) is ≥ -0.75 g/dL, see Section 0. In other words, a non-inferiority margin of -0.75 g/dL will be used in the Hb efficacy assessments.

Support for the use of a non-inferiority margin of -1.0 g/dL in the peginesatide submission for the dialysis studies was initially provided by estimating the magnitude of the effect of erythropoietin analogue therapy. This estimate was based on summary information from the darbepoetin alfa development program ([Aranesp 2001](#), [Omontys 2012](#)), with publicly available summary data. Based on these data, the estimated treatment effect of erythropoietin analogue therapy in the dialysis population was approximately 2.0 g/dL. Based on these data, the estimated treatment effect of erythropoietin analogue therapy in the dialysis population with a 10-12 g/dL target range (at least 2.0 g/dL and was considered to be appreciably larger than 1.0 g/dL, thus supporting the choice of a non-inferiority margin of -1.0 g/dL.

Therefore, the choice of -0.75 g/dL as non-inferiority is more conservative than prior programs, and consequently, an appropriate margin to use.

The comparison between the study drugs for the time-to-first instance of receiving RBC transfusion, or erythropoietin analogue (for roxadustat subjects only) as rescue therapy is also based on a NI evaluation. For this purpose, in the lack of support for the choice from the literature, a 1.8 margin has been selected. NI will thus be claimed if the upper bound of the 2-sided 95% CI for the hazard ratio (roxadustat/epoetin alfa) is less than or equal 1.8.

The analysis of the proportion of total time of Hb within the interval of 11 ± 1 g/dL from week 28 until week 52 between the treatment groups also relies on a non-inferiority evaluation. For this purpose a NI margin of -0.15 has been adopted, i.e. the 2-sided 95% CI around the difference between roxadustat and epoetin alfa has to exceed -0.15. No support from the literature has been found for this selection.

